Important medical events that may not be immediately life-threatening or result in death or hospitalization but may jeopardize the patient or may require intervention to prevent one of the other outcomes listed in the definition above should also usually be considered serious. Examples of such events include allergic bronchospasm requiring intensive treatment in an emergency room or at home, blood dyscrasias or convulsions that do not result in inpatient hospitalization, or the development of drug dependency or drug abuse.

A diagnosis of cancer during the course of a treatment should be considered as medically important. The List of Critical Terms (1998 adaptation of World Health Organization Adverse Reaction Terminology Critical Terms List, provided in the “Instructions for completing the ‘Serious Adverse Event/Expedited Report from a Clinical Trial’ form”) should be used as guidance for adverse events that may be considered serious because they are medically important.

Clarification of the difference in meaning between “severe” and “serious”

The term “severe” is often used to describe the intensity (severity) of a specific event (as in mild, moderate, or severe myocardial infarction); the event itself, however, may be of relatively minor medical

significance (such as severe headache). This is not the same as “serious”, which is based on the outcome or action criteria usually associated with events that pose a threat to life or functioning. Seriousness (not severity) serves as a guide for defining regulatory reporting obligations.

SAEs/AEs will be reported up to one month after surgery, and SAEs notification will be made within 24 hours.

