12.2 Period of Observation

For the purposes of this study, the period of observation for collection of adverse events extends from the date of signature of the informed consent until 100 days after the last day of study treatment except for adverse events related to study drug, which must be reported during follow-up period until resolution or initiation of further anti-tumor therapy.

If an Investigator detects a serious adverse event in a study subject after the end of the period of observation, and considers the event possibly related to prior study treatment, he or she should contact the Sponsor to determine how the adverse event should be documented and reported.

At each visit/assessment AEs will be assessed from information collected from the source documents and information transcribed into the CRF.

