15.2 Sample Size, Power

The maximum sample size (N) is calculated based on α , β , and the expected effect size, using a test for single binomial proportion for a two-stage design with a 1:1 randomization and O'Brien-Fleming (OF) stopping rules, allowing for early stopping for futility after Stage I. The software East 6.0 was used.

The rate of complete resection equal to or lower than 85% (P0) is considered as unacceptable after immune treatment. On the other hand, we can conclude to a good rate of complete resection if it is 95% (P1). The computation is based on the following assumption, considering the probability of compliance: P0 =85%; P1 = 95%; statistical power of 0.90; type I error rate (one-sided) of 0.05.

The null hypothesis that the rate of complete resection is P0 = 85% will be tested against a one-sided alternative. In the first stage, 39 patients will be accrued. If there are 34 or fewer responses in these 39 patients, the study will be stopped for futility. Otherwise, 38 additional patients will be accrued for a total of 77. The null hypothesis will be rejected if 71 or more responses are observed in 77 patients. To take into account 5% of ineligible patients, 81 patients will be included.

Duration of accrual: 18 months and 1 year follow-up.

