15.5 Safety Monitoring

All patients who receive at least one dose of MEDI4376 will be included in the safety analysis. Descriptive summary tables will be presented on safety parameters

Immune adverse events of special interest will be analysed including: pneumonitis, endocrinopathies, dermatologic (rash/pruritus) and hepatic (elevation of transaminases/bilirubin).

The number of post-operative events and a tolerance report will be achieved on the first 15 patients to discuss the pursuit of the trial.

A definitive discontinuation of the study in real time is planned in case of occurrence of a new death (any cause combined) occurring within 90 days of the intervention among the 12 consecutive first patients enrolled after the resuming of the trial (46th patient and the following).

Tolerance data (90-day postoperative follow-up) for these 57 patients will be analyzed by the steering committee.

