16.4.1 Study schedule

The protocol should begin at 2nd quarter of 2016. The trial recruitment period is expected to be 32 months, follow-up is one year. The trial should be ended by mid-June 2020.

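### The 90-day death stop ends at patient 57 with no stated criterion for patients 58 to 81, and the two reporting windows conflict and do not reliably reach day 90

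*Protocol*

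**What the plan says.** Protocol section 15.5 contains the rule: "A definitive discontinuation of the study in real time is planned in case of occurrence of a new death (any cause combined") within 90 days of the operation, "among the 12 consecutive first patients enrolled after the resuming of the trial (46th patient and the following"). The next sentence reads: "Tolerance data (90-day postoperative follow-up) for these 57 patients will be analyzed by the steering committee". It gives no criterion for that review and does not say whether inclusion waits for it.

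The planned total is in section 15.2: "To take into account 5% of ineligible patients, 81 patients will be included". Two recruitment periods are given: "Duration of accrual: 18 months and 1 year follow-up" in section 15.2, and "The trial recruitment period is expected to be 32 months, follow-up is one year" in section 16.4.1.

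On reporting, section 12.1.1 closes with: "SAEs/AEs will be reported up to one month after surgery, and SAEs notification will be made within 24 hours". Section 12.2 instead sets the collection period from consent "until 100 days after the last day of study treatment except for adverse events related to study drug"; drug-related events are followed for longer. Section 10.1 places surgery 2 to 14 days after the last infusion. Sections 9.2 and 13.5 schedule visits at 4 weeks, 6 months and one year after surgery.

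**The concern.** The trial was resumed under a strict mortality rule, in which a single death among 12 patients ends it. For the remaining patients the protocol states no threshold at all, and the review that closes the 12-patient period depends on data that mature about four months after the 57th inclusion. An excess of deaths can by chance pass a zero-death check on 12 patients and then meet no pre-stated boundary.

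The rule also needs to learn of deaths promptly up to day 90 after surgery. If the reporting sections close earlier, or disagree on when they close, the rule may lack the events it acts on. That would affect patients 46 to 57 as well.

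**Working it through.** **The plan's total.** From 77 evaluable patients and 5% ineligible, 77 × 1.05 = 80.85, rounded up to 81; dividing gives 77/0.95 = 81.05. The boundaries of 34 of 39 and 71 of 77 give an exact one-sided error of 0.042 and power of 0.895, close to the stated 0.05 and 0.90. The figure of 81 is a sound base.

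**Scope of the death rule.** Twelve patients starting with the 46th end at 46 + 12 - 1 = 57, which matches the 57 patients of the review (45 + 12). Patients outside the rule: 81 - 57 = 24, and 24/81 = 30%. The other looks do not fill the gap. The tolerance report on the first 15 patients precedes the restart, and the only other numerical stop (39 patients, section 15.2) concerns complete resection.

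**Lag to the 57-patient review**, from inclusion of patient 57:
- inclusion to first infusion: 0 to 7 days (section 5.1, criterion 11)
- first to last infusion: 28 days (days 1, 15 and 29, section 4)
- last infusion to surgery: 2 to 14 days (section 10.1)
- postoperative window: 90 days

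Shortest: 0 + 28 + 2 + 90 = 120 days. Longest: 7 + 28 + 14 + 90 = 139 days. At 30.44 days per month this is 3.94 to 4.57 months.

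**Patients included during the lag** = accrual rate × lag, assuming constant accrual and no pause:

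| Recruitment period | Rate per month | Included of the last 24 | Share |
|---|---|---|---|
| 18 months (15.2) | 81/18 = 4.50 | 17.7 to 20.6 | 74-86% |
| 32 months (16.4.1) | 81/32 = 2.53 | 10.0 to 11.6 | 42-48% |

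Section 8 allows 7 working days to the first infusion. This lengthens the longest lag to about 143 days and gives 21.1 and 11.9 patients. If the 32 months contain a 6-month suspension (an assumption; its length is not given), the rate is 81/26 = 3.12 per month and the share 51-59%.

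**What the 12-patient check can exclude.** The documents give no mortality rate, so these rates are assumptions.

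| True 90-day mortality p | Rule stops the trial, 1 - (1 - p)^12 | Rule is passed | Expected deaths in the next 24 if passed |
|---|---|---|---|
| 2% | 0.215 | 0.785 | 0.48 |
| 5% | 0.460 | 0.540 | 1.2 |
| 10% | 0.718 | 0.282 | 2.4 |

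At 10%, allowing for the chance that the trial has already stopped, the expected number is 0.282 × 2.4 = 0.68.

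**Reporting windows against day 90.** Under section 12.1.1 reporting ends about one month after surgery, leaving roughly days 31 to 90 uncovered. Under section 12.2, taking the last infusion as the last study treatment, the closing postoperative day is 100 minus the gap to surgery:
- gap of 2 days: day 98
- gap of 10 days: day 90
- gap of 14 days: day 86, which is 4 days short

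No visit falls between 4 weeks and 6 months after surgery, so no scheduled contact would reveal a death in that interval before the 6-month visit.

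**The case against.** A reader might infer that any number of deaths among patients 58 to 81 would have no consequence. The documents do not support that. Section 16.4.2 lets the sponsor and coordinating investigator end the study, section 16.5 gives the steering committee all decisions on its execution, and section 6 requires each inclusion to be validated beforehand. What is missing is a pre-stated criterion, not oversight.

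A reader might also infer that deaths among patients 46 to 57 go unanswered until the late review. They do not, because the rule acts in real time. If the review takes place as planned, no such death has occurred in those 12, so it adds little on their mortality. The delay mainly concerns non-fatal tolerance and the absence of an inclusion hold.

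Nor is it established that most of the last 24 are included before the review. Under the 32-month period without a pause the share is just under half.

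It is also tempting to say that deaths from day 31 to day 90 need not be notified within 24 hours. That holds only if section 12.1.1 governs. If section 12.2 governs, sections 12.3 and 12.4 make serious events in its period immediately reportable, the shortfall is at most 4 days, and drug-related events have longer cover. The rule, however, counts deaths from any cause, so that exception does not close the gap.

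Finally, a zero-death check followed by committee review is a recognisable staged design, and a boundary for later patients is partly the sponsor's choice. This stands, and it is why the point asks for a stated decision and not for a particular boundary.

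Reading the words about the 46th patient and those after as extending the rule beyond patient 57 does not help, because the same section says 12 patients and then 57.

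**Conclusion.** The point holds in two parts.

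**Reporting windows.** These are wrong as written. Sections 12.1.1 and 12.2 contradict each other, and neither guarantees the 90 days that section 15.5 relies on. The uncovered interval is about two months under the first and up to 4 days under the second, for surgery within the planned 2 to 14 days.

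**Scope of the rule.** No mortality criterion and no inclusion hold is stated for 24 of 81 patients (30%), who are left to discretionary powers. Between 42-48% and 74-86% of them are included before patient 57 completes 90 days, depending on which of the two conflicting recruitment periods applies. These shares rest on constant accrual and no pause; a suspension inside the 32 months would raise the lower range. Whether a boundary is needed is a design trade-off that the sponsor must settle and state.

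**What to change.** 1. Reconcile the end of section 12.1.1 with section 12.2 so that deaths from any cause are notified within 24 hours through at least day 90 after surgery, and add a day-90 vital-status check. The window should be counted from surgery, as the stopping rule is.
2. State in section 15.5 whether a pre-specified mortality criterion, an inclusion hold pending the 57-patient review, or neither applies to patients 58 to 81. If a criterion is chosen, the sponsor sets the threshold and gives its operating characteristics. The existing 12-patient rule can stay unchanged.
3. Align the 18-month and 32-month recruitment periods, since the timing of the review depends on them.

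The cost is a protocol amendment, which section 16.3.3 sends to the ethics committee and the authority if substantial, plus one vital-status contact per patient. A boundary adds some chance of stopping at acceptable mortality, and its size depends on the threshold. As an illustration only, a trigger at the second death among 24 patients would fire with probability 8%, 34% and 71% at true rates of 2%, 5% and 10%.

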16 ADMINISTRATIVE SECTION

16.1 Sponsor obligations

16.1.1 Before the trial

The sponsor will:

- Ensure regulatory requirements are met before the trial is implemented
- Ensure that all administrative procedures are in place for each department in the associated establishments
- Provide the complete protocol and its appendices, the adverse event report form, CPP (Independent ethics committee) permission, statement of insurance and authorisation from the French health authority (ANSM).

The sponsor and their representatives will:

- Provide centres with the instructions and documents needed to conduct the trial properly (protocol, data collection form and investigator file)
- Organise an orientation session to train study investigators and coordinators (during this session, all protocol sections will be reviewed and how to fill out case report forms and study procedures will be explained)

16.1.2 During the trial

The sponsor and their representatives will:

- Regularly visit the investigating centres
- Be available at all times for consultation and remain in contact with the personnel of the investigating centre by email, telephone and/or fax
- Examine and evaluate the data in the case report form and look for possible errors in data collection

In cooperation with the principal investigator, the sponsor will provide all of the investigators involved with the study with any new information that may interfere with conducting the trial.

16.1.3 In terms of the trial

It is the sponsor's responsibility to make sure that the procedures are completed at the end of the trial.

16.2 Investigator obligations

The investigator agrees to conduct the study in compliance with the 1974 Declaration of Helsinki, revised in 1975 and 1989, good clinical practice, and effectual French regulations.

In regards to the French law of 9 August 2004, the investigator from each centre agrees to collect the informed written consent from each patient participating in the trial. One copy of the consent form will be given to the patient and the other will be kept in the patient's clinical file. Patients must be able to give their informed consent freely and not be under guardianship or suffer from any type of mental impairment that may affect their judgement.

The investigator also agrees to fill out the case report form needed for study follow-up.

The investigator also agrees to:

- Inform the sponsor of any serious or unexpected adverse event occurring during the trial within the time periods described in chapter 7.1 using the appropriate form.
- Agree to monitoring with access to source documents to validate data from the case report forms and if needed, agree to an internal or external audit by the sponsor or a representative from the regulatory authorities
- Archive trial documents (copies of case report forms, written consent forms) for a period of at least 15 years
- Include at least one patient during the first six months following the trial's implementation
- Make sure that there is no interference with another trial for the same indications
- Respect the confidentiality of the documents provided

16.3 Ethical considerations

16.3.1 Participant information and consent

Before conducting this biomedical research on a person, they must provide their **free, informed** and **express** consent after being informed of the purpose of the research, the study procedures and duration, the benefits, and potential risks and constraints of the study, as well as the type of product being researched and the opinion of the CPP (art. L.1122-1).

The patient and investigator or representing physician will personally date and sign the consent form (original copy archived by the investigator, a copy will be given to the patient or their legal representative).

16.3.2 Request for CNIL authorisation for automated data processing

This biomedical research will produce scientific information. This coded, directly or indirectly personal information is part of the legal framework of file use (Law n° 78-17 from 6 January 1978 and law n° 94-548 from 1 July 1994)

The sponsor (IFCT) has authorisation (n°1227585) to process personal data for the purpose of Biomedical Research on medication and diseases under the law of 20 December 1988 modified by law n° 2004-806 of 9 August 2004.

To the extent that this biomedical research is conducted within the strict regulatory and legal requirements (the "Huriet-Sérusclat" law of 20 December 1988 modified by law n° 2004-806 of 9 August 2004) and according to standard methods, the CNIL has adopted a standard method (MR001 according to article 54 from the law of 6 January 1978 modified), which now covers all personal data processing conducted as part of biomedical research - including pharmacogenetic trials - as defined in the public health code, and commitment to comply with said method.

16.3.3 Amendment and additional clauses procedures

The study's principal investigator or sponsor will suggest any substantial change in the protocol, and will then inform the other party. This will be an amendment submitted to the CPP and AFSSAPS. No change can be made without agreement from the committee. The sponsor will inform each investigator and send them the amendment and related statement of intent.

16.4 Quality control and assurance

Regulatory considerations: medical procedures for this trial comply with the most recent recommendations from the Declaration of Helsinki and public health law no. 2004-806 of 9 August 2004 related to the protection and safety of humans.

Confidentiality: the protocol and its appendixes, as well as all of the data, are confidential as noted at the beginning of the protocol.

Data monitoring: The IFCT's Clinical Research Unit will monitor this trial in order to ensure accurate, complete and reliable data collection. It will also provide logistical support to investigating centres. An inspection by an employee obligated to professional secrecy mandated by Regulatory Authorities may be required to ensure that all of the source documents needed are available and that the clinical trial is being conducted according to Good Clinical Practices and the law from 9 August 2004.

16.4.1 Study schedule

The protocol should begin at 2nd quarter of 2016. The trial recruitment period is expected to be 32 months, follow-up is one year. The trial should be ended by mid-June 2020.

16.4.2 Early study termination

The sponsor and coordinating investigator will issue any early termination of the study. The sponsor will provide written notification. This letter will be sent to the Competent Authority (ANSM) and to each investigator, as well as the CPP.

16.4.3 Statement of commitment

New investigators

Investigators can only participate in the trial after submitting a written request to the sponsor. It should include the following items:

- A statement of commitment indicating the expected number of patients that the investigator can include in the protocol per year
- A recent CV with French medical board registration number

Site opening

Before inclusions can begin, a site must be officially opened; in other words, the investigator's name, institution, telephone and fax number, and email address must be duly issued to the sponsor, CPP and Ministry (initial and additional authorisation statement). The investigator must have all of the documents needed to conduct the trial properly (protocol, investigator brochure, case report form). He must have obtained agreement from the facility's pharmacist to distribute treatments and resolve any problems with the study coordinator. He must have informed the director of his facility by letter of his participation. An agreement must be signed between the director of his facility and the sponsor.

16.5 Study organisation

The Steering Committee makes all of the decisions concerning the study's implementation, execution, analysis and reporting. It meets three times per year two times, and periodically sends information on the study's progress to investigators.

It is comprised of members of the editorial board, study statisticians and a sponsor representative.

The Coordination Centre will be the Clinical Research Unit (Unité de Recherche Clinique - URC) of the IFCT, located at [name]. Its purpose is to ensure that the trial is being conducted as intended in the protocol: patient inclusion management, data collection, data management, SAE management, organisation of investigator and committee meetings. It informs the Steering Committee of any issues concerning the trial's progress.

Moreover, the Steering Committee can organise regular investigator meetings during which the files of included patients will be reviewed. The purpose of this review panel will be to jointly verify compliance and

understanding of the eligibility criteria and treatment methods dictated by the protocol. In addition, it will conduct a progress analysis for retrospective validation.

17 FINAL REPORT AND PUBLICATIONS

Once the study is finished, a clinical trial report will be published by the study's principal investigators and statistician. The coordinating investigator will sign the final version of the clinical trial report for this study, and by doing so will indicate his approval of the report's analyses, results and conclusions.

The key participants in a clinical study are the principal investigator, investigators, IFCT-employee team members, and members of the management and scientific boards who all collaborate to various degrees from designing the trial to writing the final report.

1. The coordinator can choose between first and last place. In both cases, he must have participated significantly in designing the trial, inclusions and writing the article.
2. If the investigator chooses the first place, last place goes to the president, one of the secretaries, or one of the other elected members of the Management Board or Scientific Council. The person must be chosen based on their participation in designing the trial, inclusions and writing the article. If there is difficulty in choosing this person, a secret vote by the management board will decide.
3. If the investigator chooses the last place, the next-to-last place goes to the president, one of the secretaries, or another elected member of the Management Board or Scientific Council under the same conditions, unless he/she takes the first position if, in agreement with the principal investigator, he writes the article. If there is difficulty in choosing this person, a secret vote by the management board will decide.
4. Investigators appear by the order in which eligible patients were included. All other investigators must appear in a list in the appendix.
5. Two members of the same team cannot sign the same article unless one of them appears as a coordinating investigator, Management Board member, or Scientific Council member signing as such in first, second, or next-to-last place.
6. Members of the IFCT employee team play a vital role in clinical studies. For this reason, those who were involved in designing the trial, managing it or writing the article must systematically appear in the acknowledgements or as signatories. The director will provide their names to the principal investigator (coordinator). If they appear as signatories, they cannot be included in the first six or last two positions. There can be no more than two if the number of signatories is more than 10 and only one if the number is equal to or less than 10.

7. If a university statistician has worked on developing or processing trial data, he can sign with the approval of the principal investigator (coordinator) in a place on which they both agree (generally 3rd or 4th place).
8. Under no circumstances can someone sign for having provided a patient with routine care that was unrelated to the research.
9. All investigators (one per IFCT investigating centre) will be listed after each article in a table that may also include pathologists, surgeons and radiation therapists from the centre based on the article, so that this citation appears on Medline.
10. For ancillary studies (biological, radiology, or others), if the article or abstract has a maximum of 10 signatures, the principal investigator (coordinator) of the biological study can choose between first and last position. In both cases, he must have participated widely in the study's design, financing, inclusions and writing the article. The rules above apply to last position if he chooses last position. Next-to-last place can go to the research lab director who contributed most to the study. The last but two place can go to the study's principal investigator (coordinator) if it is not taken by the biological study's principal investigator. The first four places can be taken by scientists or physicians, with the IFCT or not, who contributed the most to the ancillary study. This may also include the university statistician if suggested by the coordinating investigator and management board office, and validated by the management board. If there are a maximum of 10 signatures, three to four places in the middle will be reserved for the best clinical contributors (in the sense that they contributed the most in terms of pathology specimens). In the case of articles with 20 signatures, two to three places will be reserved for pathologists who contributed the most to the study (either in collecting specimens or reviewing the IFCT's pathology panel). All of the labs that participated in the study shall be represented by one signatory, the remaining signatory places must be attributed to clinicians according to the rules above, including one permanent member of the IFCT team who contributed the most to the study (decision made by the CI + Director + President), as well as the CI for the clinical study.
11. All articles should include the mention "..on behalf of IFCT" at the end of the signatories list, and include the acronym IFCT-XXYY in the title of the clinical trial to which the ancillary study is related.
12. The IFCT can receive assistance with the English formatting of an article, but can never delegate the writing itself to an agency or industry.

These rules were created and validated by the IFCT Management Board in September 2010.

